8.2. Events or outcomes not qualifying as adverse events or serious adverse events

Not applicable.

8.3. Detecting and recording adverse events and serious adverse events

8.3.1. Time period for detecting and recording adverse events and serious adverse events

All AEs starting within 31 days following administration of Dose 1 and Dose 2 of the HRV vaccine (Day 1 to Day 31) must be recorded into the appropriate section of the eCRF, irrespective of intensity or whether or not they are considered vaccination-related.

The time period for collecting and recording SAEs will begin at the receipt of study vaccines until the subject is discharged from the study. See Section [8.4](#) for instructions on reporting of SAEs.

All AEs/SAEs leading to withdrawal from the study will be collected and recorded from the time of the receipt of study vaccines.

In addition to the above-mentioned reporting requirements and in order to fulfil international reporting obligations, SAEs that are related to study participation (i.e., protocol-mandated procedures, invasive tests, a change from existing therapy) or are related to a concurrent GSK medication/vaccine will be collected and recorded from the time the subject consents to participate in the study until she/he is discharged from the study.

An overview of the protocol-required reporting periods for AEs and SAEs is given in [Table 12](#).

Table 12 Reporting periods for collecting safety information

Event	Pre-V1*	Visit 1	7 d	30 d	Visit 2	7 d	30 d	Visit 3	7 d	30 d	Visit 4	ESFU contact
			post-V1	post-V1		post-V2	post-V2		post-V3	post-V3		
		Day 1			Month 2			Month 4			Month 5	Month 10
Solicited general AEs			■	■		■	■					
Unsolicited AEs			■	■	■	■	■					
AEs/SAEs leading to withdrawal from the study			■	■	■	■	■	■	■	■		
SAEs			■	■	■	■	■	■	■	■		
SAEs related to study participation or concurrent GSK medication/vaccine			■	■	■	■	■	■	■	■		

* i.e., consent obtained. V: vaccination; Post-V: post-vaccination.

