5.5. Outline of study procedures

The list of study procedures is detailed in [Table 4](#).

Table 4 List of study procedures

Age	6-12 weeks	~4 months	~6 months	~7 months	~12 months
Epoch	Epoch 001				
Type of contact	Visit 1	Visit 2	Visit 3	Visit 4	ESFU (Phone contact)
Time-points	Day 1	Month 2	Month 4	Month 5	Month 10
Sampling time-points	Pre-Vacc			Post-Vacc	
Informed consent	●				
Check inclusion/exclusion criteria	●				
Collect demographic data	●				
Record gestational age	●				
Medical history	●				
Hepatitis B vaccination history	●				
History of previous vaccination from birth other than Hepatitis B vaccination	●				
Physical examination including length and weight measurement	●				
Check contraindications and warnings and precautions to vaccination	●	●	●		
Pre-vaccination body temperature	●	●	●		
Vaccines					
Randomization and treatment number allocation	●				
Treatment number allocation for subsequent doses		●	●		
Recording of administered treatment number	●	●	●		
HRV vaccine administration	●	●			
Record regurgitation	●	●			
HRV vaccine replacement dose administration in case of regurgitation*	●	●			
Co-administration of Pediarix, Hiberix and Prevenar 13	●	●	●		
Lab Assays					
Blood sampling for antibody determination (~5 mL)				●	
Safety Assessments					
Distribution of diary cards	0	0			
Record any concomitant medications/vaccinations	●	●	●	●	
Record any intercurrent medical conditions	●	●	●	●	
Recording of solicited adverse events within 8 days after each dose of HRV vaccination (Days 1-Day 8)	●	●			
Recording of non-serious adverse events within 31 days after each dose of HRV vaccination (Days 1-31)	●	●			
Recording of AEs/SAEs leading to withdrawal from study	●	●	●	●	●
Recording of SAEs	●	●	●	●	●
Recording of SAEs related to study participation, or to a concurrent GSK medication/vaccine	●	●	●	●	●
Return of diary cards		0	0		

Age	6-12 weeks	~4 months	~6 months	~7 months	~12 months
Epoch	Epoch 001				
Type of contact	Visit 1	Visit 2	Visit 3	Visit 4	ESFU (Phone contact)
Time-points	Day 1	Month 2	Month 4	Month 5	Month 10
Sampling time-points	Pre-Vacc			Post-Vacc	
Diary card transcription by investigator or designee		•	•		
Phone Contact					•
Study Conclusion					•

- is used to indicate a study procedure that requires documentation in the individual eCRF.
- is used to indicate a study procedure that does not require documentation in the individual eCRF.

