8.5. Follow-up of adverse events and serious adverse events**8.5.1. Follow-up during the study**

After the initial AE/SAE report, the investigator is required to proactively follow each subject and provide additional relevant information on the subject's condition to GSK Biologicals (within 24 hours for SAEs; refer to [Table 15](#)).

All SAEs documented at a previous visit/contact and designated as not recovered/not resolved or recovering/resolving will be reviewed at subsequent visits/contacts until the last visit of the subject.

All AEs documented at a previous visit/contact and designated as not recovered/not resolved or recovering/resolving will be reviewed at subsequent visits/contacts until 30 days after the last vaccination.

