8.5.2. Follow-up after the subject is discharged from the study

The investigator will follow subjects:

- with SAEs, or subjects withdrawn from the study as a result of an AE, until the event has resolved, subsided, stabilised, disappeared, or until the event is otherwise explained, or the subject is lost to follow-up.

If the investigator receives additional relevant information on a previously reported SAE, he/she will provide this information to GSK Biologicals using a paper/electronic Expedited Adverse Events Report and/or pregnancy report as applicable.

GSK Biologicals may request that the investigator performs or arranges the conduct of additional clinical examinations/tests and/or evaluations to elucidate as fully as possible the nature and/or causality of the AE or SAE. The investigator is obliged to assist. If a subject dies during participation in the study or during a recognised follow-up period, GSK Biologicals will be provided with any available post-mortem findings, including histopathology.

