9.2.2. Subject withdrawal from study vaccines

A ‘withdrawal’ from the study vaccines refers to any subject who does not receive the complete treatment, i.e., when no further planned dose is administered from the date of withdrawal. A subject withdrawn from the study vaccines may not necessarily be withdrawn from the study as further study procedures or follow-up may be performed (safety or immunogenicity) if planned in the study protocol.

Information relative to premature discontinuation of the study vaccines will be documented on the Vaccine Administration page/screen of the eCRF. The investigator will document whether the decision to discontinue further vaccination/treatment was made by the subject’s parent(s)/LAR(s), or by the investigator, as well as which of the following possible reasons was responsible for withdrawal:

- SAE
- Unsolicited non-serious AE
- Solicited AE
- Not willing to be vaccinated
- Other (specify)

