6.1. Demography

6.1.1. Analysis of demographics/baseline characteristics planned in the protocol

The median, mean, range and standard deviation of age (in weeks) at each study vaccine dose and of the gestational age will be computed by group. The median, mean and standard deviation of length (in centimeters) and weight (in kilograms) at Visit 1 will be computed by group. The racial and sex composition of the subjects will be presented.

The distribution of subjects enrolled among the study centers will be tabulated as a whole and per group.

The number of subjects who withdraw from the study will be tabulated by group according to the reason for drop-out.

The deviations from specifications for age and intervals between study visits will be tabulated by group.

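### A non-serious AE that ends the vaccine series in an infant who stays in the study needs no AE record if it starts after Day 31, and can miss scheduled follow-up if it starts earlier

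*Protocol*

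**What the plan says.** **Collection.** Protocol 8.3.1 has an entry rule for the eCRF, which begins "All AEs starting within 31 days following administration of Dose 1 and Dose 2 of the HRV vaccine (Day 1 to Day 31) must be". For serious AEs (SAEs), "The time period for collecting and recording SAEs will begin at the receipt of study vaccines until the subject is discharged from the study". The only other rule that reaches non-serious AEs outside the 31-day windows is "All AEs/SAEs leading to withdrawal from the study will be collected and recorded from the time of the receipt of study vaccines". Table 4 in 5.5 carries the matching row, "Recording of AEs/SAEs leading to withdrawal from study", and has no row for AEs that stop vaccination.

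**Stopping vaccines and leaving the study.** Section 9.2.2 says that "A subject withdrawn from the study vaccines may not necessarily be withdrawn from the study as further study procedures or follow-up may be performed". It requires the reason for stopping on the Vaccine Administration screen, and the choices include a non-serious unsolicited AE. Section 6.5 lets an infant barred from further doses continue other study procedures. Under 9.1, an infant who is reached at the concluding contact has completed the study, whatever number of doses was given.

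**Follow-up.** Under 8.5.1, unresolved AEs "will be reviewed at subsequent visits/contacts until 30 days after the last vaccination". Section 8.5.2 requires longer follow-up for subjects "with SAEs, or subjects withdrawn from the study as a result of an AE, until the event has resolved" or is stable or otherwise explained.

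**Reporting.** SAP 6.1.1 says: "The number of subjects who withdraw from the study will be tabulated by group according to the reason for drop-out". SAP 6.2.2 adds a count of doses by group. SAP 5.2.2.1 assigns elimination code 1070 to incomplete courses.

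**The concern.** AEs that lead to discontinuation of a vaccine series are a basic tolerability result, and safety of the study vaccines is a secondary objective. The plan attaches both its out-of-window collection rule and its follow-up-to-resolution rule to leaving the study, and not to stopping the vaccines.

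Two infants with the same non-serious event, both stopped, can therefore be documented differently. The one who leaves the study has an AE record and is followed until the event settles. The one who stays may have only a ticked reason. Any count by arm of AEs leading to vaccine discontinuation, with term, grade, causality and outcome, could then be incomplete.

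**Working it through.** The plan states no figure on this point, so there is none to reproduce. The check compares the rules and counts days.

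**Inputs**
- AE window: Day 1 to Day 31 after HRV Doses 1 and 2 (Protocol 8.3.1). The dose day is Day 1, so Day 31 is 30 days after the dose.
- Optimal spacing: 60 days for Visit 1 to Visit 2 and for Visit 2 to Visit 3 (Table 5).
- Allowed spacing for the per-protocol set: 49 to 83 days and 56 to 83 days respectively (Table 19).
- Review limit for unresolved AEs: 30 days after the last vaccination (8.5.1).

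**Step 1: days before the next dosing visit with no collection of non-serious AEs.** If the visit falls v days after the dose, the uncovered days run from 31 to v − 1, which is v − 31 days.

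| Interval | v | v − 31 | Share of v |
|---|---|---|---|
| Either, optimal | 60 | 29 | 48.3% |
| Visit 1 to 2, shortest | 49 | 18 | 36.7% |
| Visit 2 to 3, shortest | 56 | 25 | 44.6% |
| Either, longest | 83 | 52 | 62.7% |

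These are shares of calendar time, not of events. After Visit 3 no study dose remains to be withheld. Only the Visit 1 to Visit 2 interval can affect an HRV dose, because Visit 3 includes only the routine vaccines.

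**Step 2: what must be recorded for an event in that gap.** Take a non-serious AE that starts on Day 32 or later, stops the series, and leaves the infant in the study.
- The 31-day rule does not apply (onset too late).
- The SAE rule does not apply (not serious).
- The withdrawal rule does not apply (infant still in the study).
- Section 9.2.2 applies and yields a reason category.
- Section 6.8 may apply and yields an intercurrent-condition entry up to Visit 4.

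Neither of the last two requires an AE record with term, grade, causality and outcome.

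**Step 3: follow-up of an event inside the window.** Suppose a non-serious AE within 31 days of Dose 1 ends the series, so that Dose 1 is the last vaccination. The time from the review limit to the next scheduled visit is v − 30:
- earliest allowed Visit 2: 49 − 30 = 19 days after the limit;
- optimal Visit 2: 60 − 30 = 30 days after the limit.

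No scheduled visit falls inside the review period. If the same infant continues to Dose 3, the limit moves to 30 days after Dose 3, and the unresolved event is reviewed at Visits 2 and 3. The event that ended vaccination thus has less scheduled review than the one that did not. Section 8.5.2 does not close this gap unless the event is serious or the infant leaves the study.

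**Step 4: reporting.** The SAP text gives study drop-out reasons (6.1.1), doses given (6.2.2, Template 16) and per-protocol elimination reasons including code 1070 (6.1.2, 5.2.2.1). None links an incomplete course to an AE.

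**The case against.** The case against is substantial, and much of it stands.

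- **Serious events are covered.** SAEs are collected until discharge and followed to resolution whether or not the infant leaves. Most of the permanent contraindications in 6.5 follow administration closely or would normally be serious.
- **Events are not simply lost.** All AEs within 31 days of either HRV dose are recorded. Sections 9.2.2 and 6.8 leave some eCRF trace of later ones. What is missing is the structured AE record.
- **In-window events do have an outcome.** Section 8.3.3.3 requires one for every recorded unsolicited AE, and 8.5.1 opens with a general duty to follow each subject proactively. It would be wrong to infer that these events end without an outcome. The narrower point is that the outcome may stay at not resolved.
- **Solicited AEs cannot start in the gap.** They are collected on Days 1 to 8, and the glossary reclassifies later onset as unsolicited.
- **A missing listing cannot be proved.** A reader might infer from the title of Template 14, on dropouts, that AEs stopping the vaccine are listed only when the infant leaves the study. The body of that template is not in the text available, and SAP section 10 places the full list of outputs in a separate table of contents.
- **Bias between arms is conjecture.** Investigators know the arm (5.3), and whether a stopped infant continues other procedures is at their discretion (6.5). Parents, who are blinded, may equally make the decision (9.2.1, 9.2.2).

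These points narrow the finding. They do not supply an AE record for the Day 32+ event, or a scheduled review for the infant stopped after Dose 1.

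**Conclusion.** The gap is real but narrow. It has two parts: no AE record is required for a non-serious event from Day 32 that stops the series in an infant who stays, and scheduled review can lapse for an in-window non-serious event that stops the series after Dose 1. The second part assumes that the last vaccination in 8.5.1 means the last dose the infant actually received. If only HRV is stopped and routine doses continue, the limit moves later.

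The number affected is probably very small, and the documents give no rate. If 0.3% to 1% of 640 infants per arm stopped for any AE (an assumption), that would be 0.003 × 640 = 1.9 to 0.01 × 640 = 6.4, or about 2 to 6 per arm. This is not the size of the gap. It includes serious events, in-window events that resolve, and infants who leave the study. A reader might infer that a lost event or two would materially change the comparison between arms; the documents do not support that. Safety is analysed descriptively, and no confirmatory objective is affected. This is a cheap improvement of low priority.

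**What to change.** 1. **Protocol 8.3.1, Table 4 and Table 12:** extend the withdrawal row so that it also covers AEs and SAEs that lead to early discontinuation of study vaccines. For that addition, collection from Dose 1 up to Visit 3 is enough, because Visit 3 is the last visit at which a dose can be withheld.
2. **Protocol 8.5.1 and 8.5.2:** record follow-up and outcome of these events on the same terms as AEs that lead to study withdrawal.
3. **SAP 6.1 and 6.4:** add a by-group table and listing of vaccine discontinuations by reason and, where the reason is an AE, by preferred term, grade and causality.

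The cost is wording in both documents, an eCRF link from the discontinuation reason to an AE record, a few extra AE records and follow-up contacts, and one more table with its listing. Doses, eligibility and the primary analysis are unchanged.

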8.3.2. Post-Study adverse events and serious adverse events

A post-study AE/SAE is defined as any event that occurs outside of the AE/SAE reporting period defined in [Table 12](#). Investigators are not obligated to actively seek AEs or SAEs in former study participants. However, if the investigator learns of any SAE at any time after a subject has been discharged from the study, and he/she considers the event reasonably related to the study vaccines, the investigator will promptly notify the Study Contact for Reporting SAEs.

8.3.3. Evaluation of adverse events and serious adverse events

8.3.3.1. Active questioning to detect adverse events and serious adverse events

As a consistent method of collecting AEs, the subject's parent(s)/LAR(s) should be asked a non-leading question such as:

'Has your child acted differently or felt different in any way since receiving the vaccines or since the last visit?'

When an AE/SAE occurs, it is the responsibility of the investigator to review all documentation (e.g., hospital progress notes, laboratory and diagnostics reports) relative to the event. The investigator will then record all relevant information regarding an AE/SAE in the eCRF. The investigator is not allowed to send photocopies of the subject's medical records to GSK Biologicals instead of appropriately completing the eCRF. However, there may be instances when copies of medical records for certain cases are requested by GSK Biologicals. In this instance, all subject identifiers will be blinded on the copies of the medical records prior to submission to GSK Biologicals.

The investigator will attempt to establish a diagnosis pertaining to the event based on signs, symptoms, and/or other clinical information. In such cases, the diagnosis should be documented as the AE/SAE and not the individual signs/symptoms.

8.3.3.2. Assessment of adverse events

8.3.3.2.1. Assessment of intensity

Intensity of the following solicited AEs will be assessed as described in [Table 13](#) and [Table 14](#).

Table 13 Intensity scales to be used by the parent(s)/LAR(s) for solicited symptoms during the solicited follow-up period

Adverse Event	Intensity grade	Parameter
Fever*		Record temperature in °C/°F using any age-appropriate route.
Irritability/Fussiness	0	Behavior as usual
	1	Crying more than usual/no effect on normal activity
	2	Crying more than usual/interferes with normal activity
	3	Crying that cannot be comforted/prevents normal activity
Diarrhea\$		Record the number of looser than normal stools/day
Vomiting§		Record the number of vomiting episodes/day
Loss of appetite	0	Appetite as usual
	1	Eating less than usual/no effect on normal activity
	2	Eating less than usual/interferes with normal activity
	3	Not eating at all
Cough/runny nose	0	Normal
	1	Cough/runny nose which is easily tolerated
	2	Cough/runny nose which interferes with daily activity
	3	Cough/runny nose which prevents daily activity

* Fever is defined as temperature $\geq 38.0^{\circ}\text{C}/100.4^{\circ}\text{F}$. The preferred location for measuring temperature in this study will be the oral cavity, the axilla and the rectum.

§ Diarrhea is defined as passage of three or more looser than normal stools within a day.

§ Vomiting is defined as one or more episodes of forceful emptying of partially digested stomach contents ≥ 1 hour after feeding within a day.

Table 14 Intensity scales for diarrhea, vomiting and fever occurring during the solicited period

Adverse Event	Intensity grade	Parameter
Diarrhea [§]	0	Normal (0-2 looser than normal stools/day)
	1	3 looser than normal stools/day
	2	4-5 looser than normal stools/day
	3	≥ 6 looser than normal stools/day
Vomiting [§]	0	Normal (no emesis)
	1	1 episode of vomiting/day
	2	2 episodes of vomiting/day
	3	≥ 3 episodes of vomiting/day
Fever	0	temperature < 38.0°C/100.4°F
	1	temperature ≥ 38.0°C/100.4°F – ≤ 38.5°C/101.3°F
	2	temperature > 38.5°C/101.3°F – ≤ 39.5°C/103.1°F
	3	temperature > 39.5°C/103.1°F

[§] Diarrhea is defined as passage of three or more looser than normal stools within a day.

[§] Vomiting is defined as one or more episodes of forceful emptying of partially digested stomach contents ≥1 hour after feeding within a day.

The investigator will assess the maximum intensity that occurred over the duration of the event for all unsolicited AEs (including SAEs) recorded during the study. The assessment will be based on the investigator's clinical judgement.

The intensity should be assigned to one of the following categories:

1 (mild) = An AE which is easily tolerated by the subject, causing minimal discomfort and not interfering with everyday activities.

2 (moderate) = An AE which is sufficiently discomforting to interfere with normal everyday activities.

3 (severe) = An AE which prevents normal, everyday activities

(In a young child, such an AE would, for example, prevent attendance at a day-care center and would cause the parent(s)/LAR(s) to seek medical advice.)

An AE that is assessed as Grade 3 (severe) should not be confused with a SAE. Grade 3 is a category used for rating the intensity of an event; and both AEs and SAEs can be assessed as Grade 3. An event is defined as 'serious' when it meets one of the pre-defined outcomes as described in Section 8.1.2.

8.3.3.2.2. Assessment of causality

The investigator is obligated to assess the relationship between study vaccines and the occurrence of each AE/SAE using clinical judgement. In case of concomitant administration of multiple vaccines/products, if possible, the investigator should specify if the AE could be causally related to a specific vaccine/product administered (i.e., investigational, control/placebo or co-administered vaccine). When causal relationship to a specific vaccine(s)/product(s) cannot be determined the investigator should indicate the AE to be related to all products.

Alternative plausible causes, such as natural history of the underlying diseases, concomitant therapy, other risk factors, and the temporal relationship of the event to the study vaccines will be considered and investigated. The investigator will also consult the IB and/or and/or SmPC and/or Prescribing Information for marketed products to determine his/her assessment.

There may be situations when a SAE has occurred and the investigator has minimal information to include in the initial report to GSK Biologicals. However, it is very important that the investigator always makes an assessment of causality for every event prior to submission of the Expedited Adverse Events Report to GSK Biologicals. The investigator may change his/her opinion of causality in light of follow-up information and update the SAE information accordingly. The causality assessment is one of the criteria used when determining regulatory reporting requirements.

Causality of all AEs should be assessed by the investigator using the following question:

Is there a reasonable possibility that the AE may have been caused by the study vaccine?

YES : There is a reasonable possibility that the study vaccines contributed to the AE.

NO : There is no reasonable possibility that the AE is causally related to the administration of the study vaccines. There are other, more likely causes and administration of the study vaccines is not suspected to have contributed to the AE.

If an event meets the criteria to be determined as 'serious' (see Section 8.1.2), additional examinations/tests will be performed by the investigator in order to determine ALL possible contributing factors for each SAE.

Possible contributing factors include:

- Medical history.
- Other medication.
- Protocol required procedure.
- Other procedure not required by the protocol.
- Lack of efficacy of the vaccines, if applicable.

- Erroneous administration.
- Other cause (specify).

